9. STUDY PROCEDURES

9.1 VISITS AND EXAMINATIONS

9.1.1 Summary

For a summary of the required procedures by visit, refer to the Study Schematic Table 9.1.1-1: Study Procedures by Visit.

CONFIDENTIAL AND PROPRIETARY

Study Protocol	Smith
----------------	-------

A Prospective, Multi-center, Randomized Controlled Study to Evaluate the Safety and Efficacy of ARCR augmented with REGENETEN™ Bioinductive Implant System in Full-thickness Tears (large or massive) Repair versus ARCR alone

Number: REGE Version: 2.0, 08 Dec 2021

Page: 54 of 134

Table 9.1.1-1: Study Procedures by Visit

Schedule of Event	Screening (Baseline) Day -60 to Day -1	Operation Day 0	2 Weeks Follow- up 14 ± 5 Days	6 Weeks Follow- up 42 ± 7 Days	3 Months Follow- up 91 ± 15 Days	6 Months Follow- up 182 ± 30 Days	N F uj
Informed Consent	X ¹						
Inclusion/Exclusion	X ²	X ²					
Demographics/Medical History/BMI	Х						
Operative/Discharge Data		X					
Oxford Shoulder Score	X				X	X	
WORC/C-WORC	X				X	Х	
Constant-Murley Score	X				X	X	
Subjective Shoulder Value	X				X	X	
EQ-5D-5L	X				X	X	
Patient Satisfaction	X				X	X	
VAS Pain Score	X		X	X	X	X	
Return to Work Questionnaire	X		X ³	X ³	X ³	X ³	
Opioid Use			X ⁴				
Reoperation			X	X	X	X	
MRI Assessment	X ²				X	Х	
Concomitant Medication/Therapy	Х	Х	Х	Х	Х	Х	
Safety Assessment (AEs, DDs)		X	Х	X	Х	X	
End of Study/Exit		X ³	X ³	X ³	X ³	X ³	

¹ Date of Informed consent may be the same day or another day before screening giving the subject enough time to consider particip ² Inclusion/exclusion confirmation will be performed at the time of screening and study procedure to confirm subject meets eligibility c be confirmed on arthroscopy using a calibrated probe. X-Ray and MRI to confirm eligibility criteria must be within 12 months of surge ³ As appropriate.

CONFIDENTIAL AND PROPRIETARY

This document contains information that is confidential and proprietary to Smith+Nephew PLC and Smith+Nephew, Inc. and is intended for use only manufacturer. It shall not be reproduced or copied in whole or in part, nor shall the contents be disclosed by any means without prior written permiss nor shall anyone make any use of it that is contrary to the expressed or implied wishes of Smith+Nephew.

TMP-CD-05-01 - Clinical Protocol-Device - Revision D.1; SOP-CD-05 Clinical Protocols

⁴ Opioid use will be documented daily from day 0 to day 14.

Study Protocol	Smith-Nephew
A Prospective, Multi-center, Randomized Controlled	Number:
Study to Evaluate the Safety and Efficacy of ARCR	REGENETEN.2020.01
augmented with REGENETEN™ Bioinductive Implant	Version: 2.0, 08 Dec
System in Full-thickness Tears (large or massive) Repair	2021
	Page: 55 of 134

9.1.2 Screening (Baseline) Visit 1 (Day - 60 to Day -1)

1. Obtain written informed consent from the subject as detailed in Section 7.5. This might be the same day or another day before screening giving the subject enough time to consider participation.

---- Do not proceed until consent has been obtained -----

- 2. Assign the subject a study ID in electronic data capture system.
- 3. Screen the subject for protocol inclusion/exclusion criteria and surgery indication. Any subject who signs an informed consent but fails to meet the eligibility criteria is considered to be a Screen Failure.
- 4. Obtain Demographic information, BMI and medical/surgical history, including information on all concomitant medications/therapies that is considered relevant.
- Obtain MRI and X-Ray (must be within 12 months of surgery) and confirm eligibility criteria. The tear size measurement may be provided by the radiography report or as determined by the Investigator.
- 6. Complete the Constant-Murley Questionnaire (Physician/Examiner completed portion).
- 7 Have the subject complete the OSS Questionnaire.
- 8. Have the subject complete the WORC/C-WORC Questionnaire.
- 9. Have the subject complete the subjective part of Constant-Murley Questionnaire.
- 10. Have the subject complete the SSV Questionnaire.
- 11. Have the subject complete the EQ-5D-5L Questionnaire.
- 12. Have the subject complete Patient satisfaction Questionnaire.
- 13. Have the subject complete Work Status for Return to Work Questionnaire.
- 14. Have the subject complete VAS pain questionnaire.

CONFIDENTIAL AND PROPRIETARY

Study Protocol	Smith-Nephew
A Prospective, Multi-center, Randomized Controlled	Number:
Study to Evaluate the Safety and Efficacy of ARCR	REGENETEN.2020.01
augmented with REGENETEN™ Bioinductive Implant	Version: 2.0, 08 Dec
System in Full-thickness Tears (large or massive) Repair	2021
versus ARCR alone	Page: 56 of 134

15. Instruct the subject to return for the Operation Visit on the scheduled date.

9.1.3 Operation – Visit 2 (Day 0)

- 1. Query subject regarding any changes in general health and the use of concomitant medications (e.g. oral or injected steroid use in last 4 weeks).
- 2. Confirm eligibility based on arthroscopic visualization of the tear and confirm size using a calibrated probe.
- 3. Assign the Randomization ID per randomization schedule. Screen Failure subjects should not be assigned randomization numbers, but their demographic information must be captured in the appropriate CRF with the reason for screen failure specified.
- 4. Commence operation as per the randomization schedule.
- 5. Collect operative and discharge data (including implant information) according to the CRF.
- 6. If any AEs, ADEs or DD are observed or reported, they must be recorded as instructed in Section 12 Adverse Events and Device Deficiencies.
- 7. Instruct the subject on proper postoperative care/procedures as per standard of care and/or Sponsor's recommendation given in section 6.2 Product Use.
- 8. Instruct the subject to document Opioid Use over the next 2 weeks on a daily basis.
- 9. Instruct the subject on follow-up procedures, including returning the treatment facility for follow-up at Visit 3 in 14 (± 5) days.

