7.3 EXCLUSION CRITERIA

Any of the following criteria will disqualify a potential subject from participation in the study:

- 1. Subjects who are unable to tolerate magnetic resonance imaging (MRI), due to psychiatric or medical contraindications.
- 2. Subjects with Samilson-Prieto osteoarthritis > 2.
- 3. Subjects with current or prior infection of the ipsilateral shoulder.
- 4. Subjects with known hypersensitivity to bovine-derived materials.
- 5. Subjects with known inflammatory arthropathy, history of inflammatory arthropathy, or chronic joint disease.
- 6. Subjects with prior shoulder surgery (not including rotator cuff repair [revision repair subject group only], biceps tenodesis/tenotomy, distal clavicle excision [DCE], subacromial decompression).
- 7. Subjects with an irreparable or partially reparable rotator cuff tear.
- 8. Subjects with a subscapularis tear requiring repair.
- 9. Subjects requiring a concomitant labral fixation procedure.
- 10. Subjects requiring a concomitant os acromiale fixation procedure.
- 11. Subjects with glenohumeral joint instability (multiple dislocations/subluxations).
- 12. Subjects with a subacromial or intra-articular injection within 3 months prior to surgery.

CONFIDENTIAL AND PROPRIETARY

Study Protocol	Smith-Nephew
A Prospective, Multi-center, Randomized Controlled	Number:
Study to Evaluate the Safety and Efficacy of ARCR	REGENETEN.2020.01
augmented with REGENETEN™ Bioinductive Implant	Version: 2, 08 Dec 2021
System in Full-thickness Tears (large or massive) Repair versus ARCR alone	Page: 39 of 134

- 13. Subjects with condition(s) that contraindicate or complicate outcome of ARCR e.g., > Hamada 3 rotator cuff arthropathy on X-ray, Goutallier atrophy > Grade 3, proximal humeral fracture or scapular fracture, avascular necrosis of the humeral head or glenoid, history of immunodeficiency disorders, history of chronic inflammatory disorders, oral or injected steroid use in last 4 weeks.
- 14. Subjects who are pregnant or breast feeding.
- 15. Subjects who are currently involved in any litigation or workers compensation claims.
- 16. Subjects who are enrolled, or plan to enroll, in another clinical trial during this study that would affect the outcomes of this study.
- 17. Subjects with a history of noncompliance with medical treatment, PT/rehabilitation, or clinical study participation.

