8.2 ALLOCATION AND BLINDING

8.2.1 Treatment Allocation

Enrolled primary subjects entering the randomized controlled part of the study will be randomized to either ARCR augmented with REGENETEN or ARCR alone. The randomization will be a 1:1 blocked scheme using an external online system to conceal allocation. The online system will assign a Randomization ID only after the subject meets all eligibility criteria. Details of the blocked scheme will be presented within the SAP.

Enrolled revision repair subjects will not be randomized. All subjects will be treated with ARCR augmented with REGENETEN.

CONFIDENTIAL AND PROPRIETARY

Study Protocol	Smith-Nephew
A Prospective, Multi-center, Randomized Controlled	Number:
Study to Evaluate the Safety and Efficacy of ARCR	REGENETEN.2020.01
augmented with REGENETEN™ Bioinductive Implant	Version: 2, 08 Dec 2021
System in Full-thickness Tears (large or massive) Repair versus ARCR alone	Page: 48 of 134

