8.4.2 Randomization

Subjects meeting all inclusion/exclusion criteria will be randomly allocated into any of two study groups in a 1:1 allocation ratio. Blocked randomization will be used to balance this allocation ratio by investigational site and overall. Randomization will be conducted through an online system. Randomization will occur and a treatment will be assigned only when subject has signed the ICF and satisfied all study eligibility criteria.

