	Added statement on how further regulatory status updates will be managed via TMP-CD-18-01.	Regulatory status updates will be expected during the duration of the study. This statement avoids the need for a protocol amendment for labelling requirement changes related to regulatory status updates.
6.5 Surgical Technique	The REGENETEN System should be used according to the surgical	Administrative.

Study Protocol	Smith-Nephew
A Prospective, Multi-center, Randomized Controlled	Number:
Study to Evaluate the Safety and Efficacy of ARCR	REGENETEN.2020.01
augmented with REGENETEN™ Bioinductive Implant	Version: 2.0, 08 Dec
System in Full-thickness Tears (large or massive) Repair	2021
	Page: 98 of 134

	technique and IFUs provided with the investigational device per Section 6.1.1.1 (removed list of outdated IFUs)	
7.1 Subject Population	Increased site number to 30 and added Netherlands and Japan	Updated with plan for new sites.
7.2 Inclusion Criteria	Relaxed screening cut-off for tear size (final eligibility remains >/=3cm)	Usual course of large or massive rotator cuff tear is to progress rather than improve. Investigators have reported seeing patients that had ineligible measurements in MRI but are actually large or massive tears once measured with the probe. Relaxing the screening cut-off reduces the chances of missing tears that are actually eligible per the tear size definition.
7.5 Informed Consent	Reference to ISO14155 version updated from 2011 to 2020 version	Administrative.
8.1 Study Design	Added competent authority for Japan and updated number of sites to 30. Increased total study duration from 42 to 48 months.	Updated with plan for new sites to achieve recruitment targets in the extended timeline.
8.1.1 Study Flowchart	The flow diagram has been updated to have the randomization process after performing repair and to include process for patients requiring re-operation. Title updated to Study Flowchart-Main Arms	Updated per feedback from sites. Tears have to be repairable to be considered eligible to doing the randomization after the repair ensures we do not randomise a patient that will end up as a "screen fail". Addition of process for revision repair added for clarity.

Study Protocol	Smith-Nephew
A Prospective, Multi-center, Randomized Controlled	Number:
Study to Evaluate the Safety and Efficacy of ARCR	REGENETEN.2020.01
augmented with REGENETEN™ Bioinductive Implant	Version: 2.0, 08 Dec
System in Full-thickness Tears (large or massive) Repair	2021

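### Section 9.1.3 assigns the arm before the cuff is repaired, while the version 2.0 flow diagram is described as assigning it afterwards; the two need to be reconciled

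*Combined protocol and SAP*

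**What the plan says.** Section 9.1.3 sets the order of the operative visit. Step 2: "Confirm eligibility based on arthroscopic visualization of the tear and confirm size using a calibrated probe". Step 3: "Assign the Randomization ID per randomization schedule", adding that screen failures should receive no randomization number. Step 4: "Commence operation as per the randomization schedule".

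Exclusion 7 in section 7.3 bars "Subjects with an irreparable or partially reparable rotator cuff tear". Section 8.2.1 says "The online system will assign a Randomization ID only after the subject meets all eligibility criteria", and 8.4.2 says "Randomization will occur and a treatment will be assigned only when subject has signed the ICF and satisfied all study eligibility criteria". Section 8.2.2 states that the study is not blinded.

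The amendment rationale (21.1.2) reports of the flow diagram in section 8.1: "The flow diagram has been updated to have the randomization process after performing repair". Its reason is "Tears have to be repairable to be considered eligible to doing the randomization after the repair ensures we do not randomise a patient" who would then turn out to be a screen failure. Section 21.1.4 repeats the change. Neither amendment table lists a change to 9.1.3.

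On analysis, section 7.6 counts as enrolled only those who met the criteria and were treated. It calls consented subjects who do not receive study treatment screen failures. Section 10.2 keeps randomised subjects in the full analysis set (FAS) whether or not they met the entry criteria, provided they were recruited and attended a post-surgery assessment. The per-protocol (PP) set drops those who did not meet the criteria.

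**The concern.** Two current parts of the plan give different moments for allocation, and sites work from both. Under 9.1.3 the surgeon learns the arm before repairing the tendon. The primary endpoint is failure of that repair on MRI at 6 months, so any difference in repair effort between arms acts directly on the outcome. Independent MRI reading (9.2.12) cannot undo a difference introduced in theatre.

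The call on exclusion 7 would also be made with the arm known, so removal of difficult tears could differ between arms. Allocation after the repair closes both routes, because the arms are then treated alike until the implant is or is not placed. In an otherwise open trial this is one of the few protections available.

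A second gap follows. The plan does not say clearly what happens to a subject who is randomised and then found not fully reparable.

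**Working it through.** No stated figure is at issue, so the main check is textual.

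| Place | Position of allocation |
|---|---|
| 9.1.3, steps 2 to 4 | After visualisation and probe sizing; no repair step precedes it |
| 8.2.1 and 8.4.2 | After all eligibility criteria are met; the repair is not mentioned |
| 7.3, exclusion 7 | Full reparability required; timing of the judgement not stated |
| Flow diagram, as described in 21.1.2 and 21.1.4 | After the repair |

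The rows for 8.2.1, 8.4.2 and 7.3 fit either order. The conflict is between the first row and the last. The last describes the revised, current figure, so this is not a comparison with superseded text.

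Fate of a subject randomised and then found not fully reparable:
- FAS (10.2): may be kept, if recruited and assessed after surgery.
- PP (10.2): dropped.
- 7.6: not enrolled, because the criteria were not met; a screen failure if no study treatment is given.

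Section 10.4.1 analyses both FAS and PP and names neither as primary.

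**Size, as illustration only.** Inputs from sections 10.1 and 11: 130 per arm, retear 15% against 30%, two-sided 5%. Fixed-design pooled z-test, ignoring the interim look:

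probability of a finding for the device = Φ[(Δ − 1.96·s0)/s1], where Δ = p2 − p1, s0 = √(2·p̄(1 − p̄)/n), s1 = √((p1(1 − p1) + p2(1 − p2))/n), and p̄ is the mean of the two rates.

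Loss of subjects from the analysis, equal in both arms (assumed 5% or 10%, that is 13 or 26 of 260):
- n = 130: s0 = 0.0518, s1 = 0.0510, Φ(0.952) = 82.9%
- n = 123.5: s0 = 0.0531, s1 = 0.0523, Φ(0.877) = 81.0%
- n = 117: s0 = 0.0546, s1 = 0.0537, Φ(0.800) = 78.8%

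Bias with no true effect (control 30%, device arm lowered by an assumed 1, 2 or 3 points through knowledge of the arm, n = 130):
- 30% against 30%: Φ(−1.960) = 2.5%
- 29% against 30%: Φ(−1.783) = 3.7%
- 28% against 30%: Φ(−1.605) = 5.4%
- 27% against 30%: Φ(−1.425) = 7.7%

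The documents give neither a rate of intra-operative non-reparability nor a size of bias.

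**The case against.** The strongest reply is that the sponsor has already settled the matter: the flow diagram was changed to randomise after the repair, for the reason given here, and one step list was left behind. That stands, and it makes this an inconsistency to repair rather than a deliberate design choice.

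Section 9.1.3 can also be defended on its own terms. Step 2 treats eligibility as confirmed by arthroscopic view, and step 3 withholds randomization from screen failures. Arthroscopy is already under way at step 2, so a site might take step 4 to mean only the arm-specific part. But nothing in the list places the repair before step 3, so the text does not secure that reading.

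Two stronger readings are tempting and are not supported. A reader might infer that 9.1.3 contradicts section 7.3 by itself, because reparability can be known only once the repair is done. Section 7.3 does not say when reparability is judged; that premise comes from the rationale in 21.1.2, and some irreparable tears may be recognised at arthroscopy. A reader might also infer that the plan as a whole excludes subjects and has repairs performed with the arm known. That follows only where sites act on 9.1.3 rather than the flow diagram, and the FAS can retain the subjects concerned.

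The power effect is small, lies around the 80% target, and comes with a sample size re-estimation at the interim. It also assumes equal loss in both arms, so it does not measure arm-dependent removal.

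**Conclusion.** The point holds as an unreconciled contradiction between 9.1.3 and the current flow diagram on whether allocation precedes or follows the repair, together with an unclear rule for subjects randomised and then found not fully reparable. It rests on the description of the flow diagram in 21.1.2 and 21.1.4, since the figure was not available.

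Where sites follow 9.1.3, the surgeon knows the arm during the repair and during the judgement on exclusion 7. Bias matters more than power: on the assumed values, power falls by 2 to 4 points, whereas an unnoticed bias of 1 to 3 points in retear takes the false-superiority rate from 2.5% to between 3.7% and 7.7%. These figures show sensitivity and do not estimate what will happen. The change is worth making because it is cheap and puts into the procedure an order that the sponsor has already adopted.

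**What to change.** Reconcile 9.1.3 with the flow diagram:
1. Confirm tear size with the probe.
2. Complete the repair and confirm all criteria, including exclusion 7.
3. Obtain the allocation.
4. Place the implant or not, as allocated.

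Sections 8.2.1 and 8.4.2 already require all criteria to be met before allocation and need no substantive change.

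State in 10.2 that any subject already randomised and then found not fully reparable stays in the FAS in the assigned arm, and word the screen-failure rule in 7.6 so that it does not remove such a subject.

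The cost is protocol wording, notice to sites, and an allocation call made later in the same operation.

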9.1.4 Postoperative Follow-up Visit 3 (2 Weeks [14 days ± 5 days])

- Query subject regarding any changes in general health and the use of concomitant medications. If any AEs, ADEs or DDs are observed or reported, they must be recorded as instructed in Section 12 – Adverse Events and Device Deficiencies.
- 2. Have the subject complete VAS pain score.
- 3. Have the subject complete the Return to Work Questionnaire (if appropriate).

CONFIDENTIAL AND PROPRIETARY

Study Protocol	Smith-Nephew
A Prospective, Multi-center, Randomized Controlled	Number:
Study to Evaluate the Safety and Efficacy of ARCR	REGENETEN.2020.01
augmented with REGENETEN™ Bioinductive Implant	Version: 2.0, 08 Dec
System in Full-thickness Tears (large or massive) Repair	2021
versus ARCR alone	Page: 57 of 134

- 4. Collect daily Opioid Use documentation from subject and enter into eCRF.
- 5. If any Reoperation occurred complete reoperation CRF.
- 6. Complete End of Study/exit information (if appropriate).
- 7. Instruct the subject on follow-up procedures, including returning the treatment facility for follow-up at Visit 4 at 42 (± 7) days.

9.1.5 Postoperative Follow-up Visit 4 (6 Weeks [42 days ± 7 days])

- 1. Query subject regarding any changes in general health and the use of concomitant medications. If any AEs, ADEs or DDs are observed or reported, they must be recorded as instructed in Section 12 Adverse Events and Device Deficiencies.
- 2. Have the subject complete VAS pain score.
- 3. Have the subject complete the Return to Work Questionnaire (if appropriate).
- 4. If any Reoperation occurred complete reoperation CRF.
- 5. Complete End of Study/exit information (if appropriate).
- 6. Instruct the subject on follow-up procedures, including returning the treatment facility for follow-up at Visit 5 at 3 months (91 ± 15 days).

9.1.6 Postoperative Follow-up Visit 5 (3 Months [91 ± 15 days)

- Query subject regarding any changes in general health and the use of concomitant medications. If any AEs, ADEs or DDs are observed or reported, they must be recorded as instructed in Section 12 – Adverse Events and Device Deficiencies.
- 2. Have the subject complete VAS pain score.
- 3. Complete the Constant-Murley Questionnaire (Physician/Examiner completed portion).
- 4. Have the subject complete the OSS Questionnaire.
- 5. Have the subject complete the WOR/C-WORC Questionnaire.
- 6. Have the subject complete the subjective part of Constant-Murley Questionnaire.
- 7. Have the subject complete the SSV Questionnaire.
- 8. Have the subject complete the EQ-5D-5L Questionnaire.

CONFIDENTIAL AND PROPRIETARY

Study Protocol	Smith-Nephew
A Prospective, Multi-center, Randomized Controlled	Number:
Study to Evaluate the Safety and Efficacy of ARCR	REGENETEN.2020.01
augmented with REGENETEN™ Bioinductive Implant	Version: 2.0, 08 Dec
System in Full-thickness Tears (large or massive) Repair	2021
versus ARCR alone	Page: 58 of 134

- 9. Have the subject complete Patient satisfaction Questionnaire.
- 10. Have the subject complete the Return to Work Questionnaire (if appropriate).
- Complete MRI assessment.
- 12. If any Reoperation occurred complete reoperation CRF.
- 13. Complete End of Study/exit information (if appropriate).
- 14. Instruct the subject on follow-up procedures, including returning the treatment facility for follow-up at Visit 6 at 6 months (182 ± 30 days).

9.1.7 Postoperative Follow-Up Visit 6 (6 Months [182 ± 30 days])

- 1. Query subject regarding any changes in general health and the use of concomitant medications. If any AEs, ADEs or DDs are observed or reported, they must be recorded as instructed in Section 12 Adverse Events and Device Deficiencies.
- 2. Have the subject complete VAS pain score.
- 3. Complete the Constant-Murley Questionnaire (Physician/Examiner completed portion).
- 4. Have the subject complete the OSS Questionnaire.
- 5. Have the subject complete the WOR/C-WORC Questionnaire.
- 6. Have the subject complete the subjective part of Constant-Murley Questionnaire.
- 7. Have the subject complete the SSV Questionnaire.
- 8. Have the subject complete the EQ-5D-5L Questionnaire.
- 9. Have the subject complete Patient satisfaction Questionnaire.
- Have the subject complete the Return to Work Questionnaire (if appropriate).
- Complete MRI assessment.
- 12. If any Reoperation occurred complete reoperation CRF.
- 13. Complete End of Study/exit information (if appropriate)
- 14. Instruct the subject on follow-up procedures, including returning the treatment facility for follow-up at Visit 7 at 12 months (365 ± 60 days).

CONFIDENTIAL AND PROPRIETARY

Study Protocol	Smith-Nephew
A Prospective, Multi-center, Randomized Controlled	Number:
Study to Evaluate the Safety and Efficacy of ARCR	REGENETEN.2020.01
augmented with REGENETEN™ Bioinductive Implant	Version: 2.0, 08 Dec
System in Full-thickness Tears (large or massive) Repair	2021
	Page: 59 of 134

